#### **10.6. Treatment Period For Efficacy Analyses**

There are 2 treatment periods for efficacy analyses.

1. The entire dosing interval (Days 1 to 28 inclusive) is the date of first dose to the last dose on day 28+24hours, or 24 hour post last dose of the study drug, whichever is earlier.
2. The steady-state or effective dosing interval (Days 8 to 28 inclusive) is the date of first dose +7 days to the last dose on day 28+24hours, or 24 hour post last dose of the study drug, whichever is earlier.

HAE attacks that occur during the treatment period will be included in all relevant efficacy data summaries.

HAE attacks that occur prior to or after the treatment period will also be summarized for the following periods: Qualification Period, screening to baseline Period and the follow-up period.

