### 5.3.3.3. Interim Efficacy Results

Interim results for the primary efficacy endpoint, number of confirmed HAE attacks, and the secondary efficacy endpoint of number of HAE attacks analyzed by anatomical location, are presented for Parts 1 and 2 as of the cut-off date of 19 May 2017.

Statistically significant and clinically meaningful reductions in the rate of attacks were observed in subjects treated with BCX7353 compared to placebo. Reductions in attack rates were observed at all doses tested, compared to placebo. In the Full Analysis Set (FAS) for the Entire Dosing Period (Days 1-28), the Least Squares Mean (LSM) attack rate for placebo was 0.898 per week,

and a reduction in the confirmed attack rate of 0.434 attacks/week (48.4%,  $p < 0.001$ ) was observed for all BCX7353 doses combined compared to placebo. Reductions in confirmed attack rates by treatment group were: 350-mg dose group  $n = 18$ , 0.384 attacks/week, 42.8% reduction compared to placebo ( $p = 0.007$ ); 250-mg dose group  $n = 6$ , 0.417 attacks/week, 46.4% reduction compared to placebo ( $p = 0.039$ ); and 125-mg dose group  $n = 7$ , 0.579 attacks/week, 64.5% reduction compared to placebo ( $p = 0.003$ ). Consistent results were observed in the Per Protocol (PP) population and during the Effective Dosing Period (Days 8-28), the duration at which study drug was at steady state.

A prespecified secondary endpoint analyzed the rate of confirmed attacks by anatomical location, specifically attacks that included abdominal symptoms versus attacks with only peripheral symptoms. This analysis identified a dose-ordered difference in attack rate by anatomical location. A differential response in attack rate reductions was observed for attacks with objective peripheral symptoms compared to attacks with abdominal symptoms, particularly at the two higher doses (250 mg and 350 mg).

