### 8.2. Subject Selection

#### 8.2.1. Inclusion Criteria

Subjects must meet all of the following inclusion criteria to be eligible for participation in this study:

1. Able to provide written, informed consent
2. Males and non-pregnant, non-lactating females age 18 to 70 years
3. A clinical diagnosis of hereditary angioedema Type 1 or Type 2 as documented at any time in the medical records or at the screening visit by a low C1 INH functional level (Type 2) or a low C1 INH antigenic level (Type 1)
4. A documented HAE attack rate of at least 2 HAE attacks per month for 3 consecutive months (defined as 93 days) within the 6 months prior to the screening visit as documented in acceptable source records.

Source records of historical HAE attacks must exist (for all subjects) that permit a qualifying HAE attack rate to be calculated. Any of the following will be acceptable source records of HAE attacks: clinic notes with a numerical rate of attacks, acute attack medicine administration records, or a historically-completed subject record of attacks. This record should indicate the dates of attacks, at a minimum.

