## 5. SAMPLE SIZE CONSIDERATIONS

Given that the BCX7353 response rate is unknown, the sample size was kept flexible to cover a range of response options that would achieve 90% power with an alpha of 0.05. The study population is expected to have a mean baseline attack rate of 1 attack/week. The expected mean reduction in attack rate of 350 mg BCX7353 QD is at least 70%. The mean reduction in attack rate in the placebo group may be as high as 30%. Sample size sensitivity assessments provided in Tables 2 and 3 are based on various BCX7353 and placebo responses and variability.

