#### **10.8. Derived Attack Endpoints**

Subject-reported attacks will be adjudicated by the independent Clinical Endpoint Adjudication Panel (CEAP). The attacks that have been confirmed by the adjudication committee will be included in efficacy analyses. The details of adjudication are provided in the CEAP charter.

The attack endpoints described in this section are based on confirmed attacks by the CEAP, however the rate of attacks will also be calculated for all subject reported attacks. Efficacy analyses will be conducted for HAE attacks reported over the entire dosing period (Days 1 to 28

inclusive), during the dosing period in which BCX7353 should be at steady-state conditions (Days 8 to 28, inclusive), and during the entire study period (Day 1 to the last HAE diary in the follow-up period).

The efficacy analyses will be calculated for 3 treatment periods:

- Entire Dosing Period  
Duration (days) = 28 or (Date of last dose –date of first dose+1), whichever is earlier
- Effective Dosing Period  
Duration (days) = 21 or (Date of last dose –date of first dose-6), whichever is earlier
- Entire Study Period  
Duration (days) = Date of last HAE Attack Diary collection during the follow-up –date of first dose

All efficacy analyses will also be run by treatment period and population (FAS or PP).

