### 10.8.1. Rate of Attacks

The primary endpoint, confirmed attack rate, is the total number of (count) confirmed attacks during the treatment period and standardized to an appropriate denominator, e.g. 7 days for a weekly attack rate. The weekly attack rate will be calculated for each subject:

$$\text{Weekly Attack Rate} = \frac{\text{Number of Attacks} * 7}{\text{Duration (days)}}$$

Number of attacks is total count of attacks reported during the respective dosing period (“Duration (days)” in the above equation]. The primary endpoint will be calculated for the entire dosing period and for the effective dosing period. The weekly attack rate will also be derived for all subject reported attacks and for confirmed attacks requiring treatment.

The attack rates will also be calculated for pre and post treatment periods:

Attack Rate from Screening to Baseline:

$$= \frac{\text{Total Number of attacks reported} * 7}{\text{Duration of the reporting period in days}}$$

Attacks with a start date after screening and before the date of first dose will be included and the duration of the reporting period is date of first dose – date of screening visit+1.

Attack Rate from date of day 29 to the last follow-up on study:

$$\frac{\text{Total Number of attacks reported} * 7}{\text{Duration of the reporting period period in days}}$$

Attacks that start greater than 24 hours after the last dose will be included. The duration of the reporting period is from the date of last dose+24 hours to the date of last follow-up.

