### **10.8.2. Number and Percentage of Subjects Who Are Attack Free**

The following attack free endpoints will be derived for each treatment period (the entire dosing period, and the effective dosing period ):

- The number and percentage of subjects who report no attacks during the treatment period for the FAS set and PP population. Subjects who report no attacks and discontinued before the end of the planned treatment period (day 28) are considered attack free.
- The number and percentage of subjects who report no attacks during the treatment period for the FAS set and PP population excluding subjects who discontinue before the planned treatment period (day 28).
- The number and percentage of subjects who report no attacks during the treatment period for the FAS set and PP population. Subjects who discontinue before the planned treatment period (day 28) are considered not attack free.

The above attack free endpoints will also be derived for the entire study period.

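### The Day 1–28 efficacy window opens at the calendar date, not the time, of first dose, so attacks that began before the first capsule count as on treatment in every arm

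*SAP*

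**What the plan says.** SAP 10.6 sets two windows for efficacy. The entire dosing period "is the date of first dose to the last dose on day 28+24hours", or to 24 h after the last dose if that comes sooner. The effective dosing period "is the date of first dose +7 days to the last dose on day 28+24hours", with the same end. SAP 10.8 adds an entire study period that also starts on Day 1.

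SAP 10.8.1 defines the pre-treatment period by date as well: "Attacks with a start date after screening and before the date of first dose will be included". An attack that starts on the date of first dose, at whatever hour, is thus outside screening and inside treatment.

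The denominator in SAP 10.8 is in whole days: "Duration (days) = 28 or (Date of last dose –date of first dose+1), whichever is earlier". The first attack-free endpoint in SAP 10.8.2 is "The number and percentage of subjects who report no attacks during the treatment period for the FAS set and PP population". SAP 12.1.1 compares attack-free proportions by Fisher's exact test.

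Elsewhere the SAP does cut by time. The general baseline in 10.3 is the last assessment before the time of first dose, and 12.4 calls an adverse event pre-dose if its onset date and time precede the first dose.

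**The concern.** The drug cannot prevent an attack that started before it was taken. Under Protocol 10.3.2 the Day 1 dose is given in clinic after an overnight fast, ECGs, blood draws and a meal, so some hours separate midnight from the first capsule. An onset in those hours is charged to the treatment period.

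The same number of pre-dose attacks is expected in each arm, but that does not make them harmless for every endpoint. They add equally to the rates, so the rate difference survives. The attack-free proportion is instead multiplied by a common factor below 1, so the arm with more attack-free subjects loses more and the difference shrinks.

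The bookkeeping is also uneven. The screening denominator in SAP 10.8.1 (date of first dose minus screening date, plus 1) already includes Day 1, yet Day 1 attacks are left out of its numerator. Day 1 is then counted again in the dosing denominator.

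**Working it through.** **Inputs**
- Hazard before any drug: "The study population is expected to have a mean baseline attack rate of 1 attack/week" (SAP 5).
- Lower bound: the entry criterion in Protocol 8.2.1, 2 attacks per month over 93 days, so 6 × 7 / 93 = 0.45 per week.
- Alternative: the interim "Least Squares Mean (LSM) attack rate for placebo was 0.898 per week" (Protocol 5.3.3.3).
- Attack-free planning values (SAP Table 3): placebo 15% to 30%, BCX7353 70% to 85%, 12 or 18 per arm, two-sided 0.05.
- Midnight to first dose: not in the documents. Assumed 9 h, range 6 to 12 h.
- Also assumed: constant hazard, and pre-dose attacks independent of later ones.

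**The plan's own figures.** Exact power of the uncorrected chi-square test reproduces all 24 cells of SAP Table 3 within 0.9 points: 85.3% against the stated 85% (15% vs 70%, n = 12) and 90.9% against 90% (20% vs 70%, n = 18). The planned Fisher test has lower power in those cells, 72.2% and 83.5%. The comparison below uses Fisher.

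**Subjects with a pre-dose Day 1 attack.** P = 1 − exp(−rate × h / 168).

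| Rate per week | h | P |
|---|---|---|
| 1 | 9 | 5.2% |
| 1 | 6 | 3.5% |
| 1 | 12 | 6.9% |
| 0.898 | 9 | 4.7% |
| 0.45 | 9 | 2.4% |

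**Subjects who lose attack-free status.** Only those with no later attack can lose it, so the loss is P × (proportion attack-free after the first dose). At 1 per week and 9 h:
- Placebo: 0.052 × 0.15 to 0.052 × 0.30 = 0.8 to 1.6 points.
- BCX7353: 0.052 × 0.70 to 0.052 × 0.85 = 3.7 to 4.4 points.
- In an arm of 18, at most 18 × 0.044 = 0.8 subjects.

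Over 0.45 to 1 per week and 6 to 12 h, the range is 0.2 to 2.1 points on placebo and 1.1 to 5.9 points on BCX7353.

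**Power of the attack-free comparison.** Take 70% versus 20% as the truth after the first dose, multiply both by 1 − P, and enumerate Fisher's test exactly.

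| Scenario | n = 18 per arm | n = 12 per arm |
|---|---|---|
| Window opens at time of dose | 83.5% | 61.0% |
| Date rule, 1 per week, 9 h | 78.7% | 55.3% |
| Date rule, factor exp(−0.4/7), i.e. 9.6 h | 78.3% | 54.9% |
| Date rule, half the hazard, 9 h | 81.1% | 58.1% |

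**Weekly rate.** Extra attacks per subject: 1 × 9 / 168 = 0.054. Over 4 weeks that is 0.013 per week in each arm. At the SAP Table 2 rates of 0.7 and 0.3 the difference stays at 0.4, and the relative reduction moves from 0.4 / 0.7 = 57.1% to 0.4 / 0.713 = 56.1%.

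**Length of window.** With 9 h before the dose, counting runs for 28 + 9/24 ≈ 28.4 days against a 28-day denominator. Opening at the time of dose restores 28 days.

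**The case against.** The strongest reply is that the effect is small, conservative and already covered. The weekly rate compared by ANOVA and ANCOVA barely moves. The SAP repeats the efficacy tables, attack-free status included, for Days 8–28, which cannot contain a pre-dose attack. That period also addresses a larger reason for early attacks: in healthy subjects steady state took 6 to 12 days (Protocol 5.3.1). All of this stands.

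The assumptions may also overstate the loss. Subjects who stay attack-free for 28 days plausibly have lower underlying rates; at 0.45 per week and 9 h, power at 18 per arm is 81.4% rather than 83.5%. Other cells lose less: for 85% versus 20% at n = 18, the 9.6 h factor takes power from 98.4% to 96.7%. Power itself has limited weight when the protocol (13.2.4) plans no formal hypotheses and the SAP (7.1) takes an estimation approach. These points limit the size but do not remove the misclassification.

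Three stronger readings are tempting and unsupported:
- *About 5% of all subjects lose attack-free status.* That is the share with a pre-dose attack. At 1 per week, a 5-point loss on placebo would need more than 30 h before the dose within a single day.
- *The rule counts against the drug specifically.* It applies to every arm and leaves the absolute rate difference essentially unchanged; only the attack-free difference shrinks noticeably.
- *Time to first attack would be negative.* SAP 12.1.4 defines it as after the first study medication, so a pre-dose onset need not be the event.

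The adjudication charter is not among the documents and could bear on how such attacks are handled.

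**Conclusion.** The concern holds as a minor point. Followed as written, SAP 10.6 and 10.8.1 count a pre-dose Day 1 attack as on treatment, a looser rule than the one the SAP applies to adverse events. Under the stated hazard and dosing-time assumptions, the consequence is a loss of attack-free status for about 1% of placebo and 4% of BCX7353 subjects and about 5 points of Fisher power in the 70% versus 20% case at 18 per arm, or roughly half that if the hazard is halved. The rate analysis is diluted only slightly. The bias is towards no difference. It reaches only the periods that start on Day 1: the entire dosing period and the entire study period. It deserves correction because attack-free status is a listed summary of the primary endpoint with its own test, and in arms this small one reclassified subject is visible.

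**What to change.** - **SAP 10.6, and the entire study period in 10.8:** count attacks whose onset date and time are at or after the time of first dose.
- **SAP 10.8.1:** assign earlier Day 1 attacks to the screening-to-baseline period. Its denominator already includes Day 1.
- **Untimed Day 1 attacks:** state that they stay on treatment. The noon imputation in SAP 10.1 achieves this only when the first dose is before noon, so it should not be left implicit.

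No new data are needed: the diary records dosing time, and SAP 10.1 already works with attack start times. The cost is a few phrases in the SAP and a date-time comparison in the program.

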#### **10.7. Assessment Windows**

Nominal times will be used for the descriptive summaries and plots of summary measures. Actual times will be used in the listings, individual concentration-time profiles, and in the calculation of PK parameters.

#### **10.8. Derived Attack Endpoints**

Subject-reported attacks will be adjudicated by the independent Clinical Endpoint Adjudication Panel (CEAP). The attacks that have been confirmed by the adjudication committee will be included in efficacy analyses. The details of adjudication are provided in the CEAP charter.

The attack endpoints described in this section are based on confirmed attacks by the CEAP, however the rate of attacks will also be calculated for all subject reported attacks. Efficacy analyses will be conducted for HAE attacks reported over the entire dosing period (Days 1 to 28

inclusive), during the dosing period in which BCX7353 should be at steady-state conditions (Days 8 to 28, inclusive), and during the entire study period (Day 1 to the last HAE diary in the follow-up period).

The efficacy analyses will be calculated for 3 treatment periods:

- Entire Dosing Period  
Duration (days) = 28 or (Date of last dose –date of first dose+1), whichever is earlier
- Effective Dosing Period  
Duration (days) = 21 or (Date of last dose –date of first dose-6), whichever is earlier
- Entire Study Period  
Duration (days) = Date of last HAE Attack Diary collection during the follow-up –date of first dose

All efficacy analyses will also be run by treatment period and population (FAS or PP).

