### **6.3. Full Analysis Set**

The full analysis set (FAS) population will include all subjects who are randomized, receive at least 1 dose of study drug, and have post baseline HAE diary data recorded. Subjects will be analyzed according to the randomized treatment. The FAS population will be the population for efficacy analyses.

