### **6.4. Per Protocol Population**

The per protocol (PP) population will include all subjects who are randomized, receive at least 90% of the planned 28-days of study drug, based on drug accountability, have post baseline HAE diary data recorded and have no significant protocol violations. Subjects will be analyzed according to the actual treatment received. The PP population will be an additional population for efficacy analyses.

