### **10.8.3. Number and Percentage of Attack-Free Days**

The number of attack-free days is the sum of the days during the dosing period for which a subject reported no attacks.

The percentage of attack-free days is derived as the total number of days during the dosing period for which subjects reported no attacks divided by the duration of the treatment.

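### The SAP's effective-period duration is zero or negative when the last dose falls before Day 8, and no rule says what to do with such subjects in the FAS

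*SAP*

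**What the plan says.** SAP 10.8.1 makes the effective period one of two periods for the main outcome: "The primary endpoint will be calculated for the entire dosing period and for the effective dosing period". The weekly rate is the count of attacks in the period, times 7, divided by the duration in days.

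The pieces of that rate are defined as follows.

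- **Denominator (SAP 10.8):** "Duration (days) = 21 or (Date of last dose –date of first dose-6), whichever is earlier".
- **Window for counting attacks (SAP 10.6):** it "is the date of first dose +7 days to the last dose on day 28+24hours, or 24 hour post last dose", whichever comes first.
- **Population (SAP 6.3):** FAS subjects must be randomized, "receive at least 1 dose of study drug, and have post baseline HAE diary data recorded". There is no minimum exposure.

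SAP 10.8.2 gives three attack-free definitions for each dosing period. Under the first, "Subjects who report no attacks and discontinued before the end of the planned treatment period (day 28) are considered attack free". The second leaves early discontinuers out. Under the third, "Subjects who discontinue before the planned treatment period (day 28) are considered not attack free". The table list in SAP 16 (Tables 14.2.1.16 and 14.2.2.16) labels the second and third as sensitivity analyses, so the first is by implication the main one.

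SAP 10.8.3 defines percent attack-free days as attack-free days "divided by the duration of the treatment", without saying which duration is meant for the effective period.

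**The concern.** The formula subtracts seven days from the day of last dose but has no lower bound. A subject who stops drug in the first week has no time in the effective period, yet remains in the FAS and therefore in the effective-period ANCOVA (Table 14.2.2.8). The stated rules then give either no value or a perfect score. A perfect score based on no observation flatters whichever arm loses subjects early. If the rule is left to programming, the choice may be made after Sponsor staff have seen unblinded interim results (Protocol 9.3.1 and 13.2.1).

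**Working it through.** **1. Reproduce the plan's own figure.** For a last dose on Day L, last dose date minus first dose date is L − 1. The effective duration is therefore min(21, (L − 1) − 6) = min(21, L − 7). For a completer, L = 28 gives 21, which matches the SAP.

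**2. Evaluate it for early stops.**

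| Day of last dose | 1 | 2 | 3 | 4 | 5 | 6 | 7 | 8 | 28 |
|---|---|---|---|---|---|---|---|---|---|
| Effective duration (days) | −6 | −5 | −4 | −3 | −2 | −1 | 0 | 1 | 21 |

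**3. Add the numerator.** The window opens at first dose plus 7 days (Day 8) and closes 24 hours after the last dose.

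- Last dose on Days 1–6: the window closes before it opens. The count is 0, and 0 × 7 divided by a negative number is 0.
- Last dose on Day 7: the denominator is 0, so the rate is undefined. An attack on Day 8 within 24 hours of the Day 7 dose could be counted, but it would also be divided by 0.

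**4. Attack-free status for Days 8–28.** A Day 1–6 stopper cannot have an attack in an empty window. The first definition counts the subject as attack-free, the second excludes the subject, and the third counts the subject as not attack-free.

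**5. What is not affected.**

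- The entire-dosing-period denominator is min(28, L), which is never below 1.
- Per-protocol subjects must "receive at least 90% of the planned 28-days of study drug", that is 0.9 × 28 = 25.2 days, so no first-week stopper is in that population.

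**6. How often it could happen.** At the interim, 18 + 6 + 7 = 31 subjects had received active drug (Protocol 5.3.3). Trough values are reported for 17 + 6 + 7 = 30 of them (Protocol Table 2). Troughs were collected from Day 14 (Protocol 5.3.3.2), so probably 0 or 1 of 31 stopped before about Day 14. Nothing comparable is given for the 20 placebo subjects. Three 350 mg subjects stopped drug for adverse events (Protocol 5.3.3.1), with no stop days stated.

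**7. Illustrative size.** Assumptions: one Day 1–6 stopper on 350 mg, n = 18, a constant Poisson rate, and the interim Days 1–28 rate applying to Days 8–28. The rate is 0.898 − 0.384 = 0.514 per week (Protocol 5.3.3.3).

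- Chance of no attack in 3 weeks: exp(−3 × 0.514) = 0.214.
- Gain in attack-free proportion: (1 − 0.214)/18 = 0.044, or 4.4 points.
- Fall in mean rate: 0.514/18 = 0.029 per week, from 0.514 to 0.485.

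For scale, 0.029/0.384 is about 7% of the interim 350 mg difference from placebo.

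**The case against.** The strongest reply is that the case may never arise, and that a sensible programmer would not divide by a negative duration. SAP 11.3 also allows computational algorithms and missing-data rules to be refined. The first point stands and limits the severity. The second does not remove the gap: permission to refine is not a rule, and the literal text gives a zero that could pass unnoticed.

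Three stronger readings are tempting, and the documents do not support them.

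- **That the effective-period rate has no planned alternative.** SAP 12.1.3 specifies rates based on completed diary days and on carrying the qualifying rate forward, and Tables 14.2.2.11 and 14.2.2.12 produce them for the effective period. The effective-period analysis is also run in the per-protocol population. These analyses do not repair the main FAS ANCOVA. Carrying the qualifying rate forward does not help if the diary continues after the drug is stopped.
- **That the attack-free analysis as a whole mishandles early stoppers.** The first and third definitions bracket the proportion. SAP 10.8.2 also derives attack-free status over the entire study period, which runs into follow-up. Wanting a further version for Days 1–28 is a preference about the estimand, not an error.
- **That one subject could shift an arm by 15 points or more.** That requires the placebo rate in an arm of 6. Placebo is pooled across parts and already had 20 subjects at the interim. At n = 20 the same formula gives (1 − exp(−3 × 0.898))/20, about 4.7 points, and 0.898/20 = 0.045 per week. Only the 62.5 mg arm is planned at about 6, and the documents give no attack rate for it.

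**Conclusion.** The point holds as a gap in a derivation for one of the two periods in which the main outcome is calculated. Followed literally, SAP 10.8 gives an undefined FAS effective-period rate for a last dose on Day 7 and a false zero for Days 1–6. The first attack-free definition gives Day 1–6 stoppers credit for a period with no observed time.

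The formula results are exact. The size is conditional: about 4.4 points and 0.03 per week for one such subject on 350 mg, under the Poisson and constant-rate assumptions. The protocol says that effective-period results were consistent with Days 1–28 but gives no figures, so applying the Days 1–28 rate is itself an assumption. That few subjects stop this early is an inference from the trough counts; the documents do not report stop days. A reader should not conclude that any reported result is wrong. Severity is minor.

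**What to change.** Add one rule to SAP 10.8, before database lock. When the last dose is before Day 8, set the effective-period weekly rate and attack-free status to missing, and likewise percent attack-free days if it uses the same denominator. Exclude the subject from the effective-period analysis and report the number excluded by arm. This keeps the period's purpose as an on-treatment, steady-state analysis.

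The cost is one sentence and one count per arm, with no new data. The downside is that a few subjects may drop out of the FAS effective-period analysis; they remain in the entire-dosing-period analysis.
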